### PARTICIPANT RIGHTS

Potential participants will be told that involvement in the study is entirely their choice and their decision will not affect their relationship with their healthcare team or impact on their care. Participants will be given the option to withdraw from the study at any time without explanation and have their data destroyed.

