### DESIGN

A two-group parallel Randomised Controlled Trial (RCT) with allocation ratio 1:1 will be conducted in accordance with the CONSORT guidelines (Schulz, Altman, & Moher, 2010); 150 patients undergoing elective surgery will be randomised to the control (standard preoperative care) or the intervention (routine preoperative care with VR) group.

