The Virtual Reality Symptom Questionnaire (VRSQ) is a valid and reliable measure used to evaluate the possible occurrence of symptoms of cybersickness, a type of motion sickness caused by exposure to VR (Sevinc & Berkman, 2020). This questionnaire assesses eight general physical side effects, (1) general discomfort, (2) fatigue, (3) boredom, (4) drowsiness, (5) headache, (6) dizziness, (7) concentration difficulties, and (8) nausea. It also assesses five visual effects (1) tired eyes, (2) aching eyes, (3) eyestrain, (4) blurred vision, and (5) difficulties focusing on a seven-point range from 0 to 6, with 0 indicating that the symptom is not present and 6 that the symptom is severe. The potential participants in the intervention group will be asked to complete the questionnaire immediately before surgery (T2). This outcome will be collected by the PhD candidate.

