# SAMPLE SIZE

Based on the previous study of Bekelis et al. (2017), a sample of 150 participants (75 per group) will give the study 80% power to detect a moderate effect size of 0.5 standard deviations between groups in the primary outcome variable, with a type 1 error rate of 5%. This calculation assumes a dropout rate of 15%.

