### **RISK AND BENEFITS**

There are possible risks associated with participating in this study include discomfort, headache, stomach awareness, nausea, vomiting, pallor, sweating, fatigue, drowsiness, disorientation, and apathy (Hicks & Durbin, 2011).; however, if the intervention is effective, people in the intervention group may experience reduced perioperative anxiety.

The participants will be monitored by the researcher continuously to assess for side effects. If a side effect occurs, the Virtual Reality session will be ceased immediately and treating doctor will be consulted.

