## DATA STORAGE

Electronic data will be kept on the password-protected in both the King Abdulaziz University Hospital research server and the University of Newcastle research server. Hard copy data will be stored in a locked cabinet in the office of the Chief Investigator. Only the named researchers will have access to the identifiable research data. The data will be kept for at least 15 years at the University of Newcastle before being destroyed as per policy and protocol (The University of Newcastle, 2020).

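### Withdrawal and data destruction are offered as a single option, so randomised patients who leave may take already collected anxiety and adverse-effect data with them

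*Protocol*

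**What the plan says.** Participant rights (section 3.3) gives one route out of the trial: "Participants will be given the option to withdraw from the study at any time without explanation and have their data destroyed". It sets no time limit, such as before randomisation or before analysis, and describes no alternative in which existing data stay in the trial.

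The neighbouring sections do not fill the gap:

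- Risk and benefits says "If a side effect occurs, the Virtual Reality session will be ceased immediately and treating doctor will be consulted". It does not say whether that patient continues with the planned assessments.
- Data storage says "The data will be kept for at least 15 years at the University of Newcastle before being destroyed as per policy and protocol". It does not mention data from patients who withdraw.
- Recruitment describes two agreement statements on the consent form, both about taking part. It mentions none about the use of data after withdrawal.

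On the analysis side, VAS-A, cortisol and heart rate are taken at T1, T2 and T3. The VRSQ is completed at T2 by the intervention group only. The Statistical plan uses a linear mixed model with arm, time, their interaction and the baseline value. The Sample size section states that "a sample of 150 participants (75 per group) will give the study 80% power" for a 0.5 SD effect, with a 15% dropout allowance. The Design section says the trial "will be conducted in accordance with the CONSORT guidelines".

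**The concern.** A patient who stops taking part normally leaves later values missing while earlier ones remain. Here the option to leave is joined to the destruction of what has already been recorded. A statistical analysis plan can say how missing values are handled, but it cannot restore values that were destroyed. The rule therefore has to be right in the protocol and the consent form.

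Two things are at stake. The first is the primary comparison. A patient who leaves between T2 and T3 would still contribute a T2 outcome to the mixed model; after erasure that patient contributes nothing. For a patient who leaves before T2, the T1 value would still help to describe the loss and to inform a sensitivity analysis; that too is gone. The second is the adverse-effect record. The VRSQ is the only named measure of VR side effects, and it is taken once, in one arm. If patients with symptoms are among those who choose erasure, their symptoms leave the record with them.

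The dropout allowance does not address this. It protects precision when patients are lost; it does not protect against loss that depends on treatment or anxiety.

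**Working it through.** **Reproducing the plan's figure.** Inputs from Sample size: effect 0.5 SD, power 80%, type 1 error 5% (taken as two-sided), dropout 15%.

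- Per arm before dropout: n = 2 × (1.960 + 0.842)² / 0.5² = 62.8, rounded up to 63.
- After dropout: 63 / 0.85 = 74.1, rounded up to 75 per arm, or 150 in total. The stated size reproduces.
- Power by normal approximation is 80.6% with 75 × 0.85 = 63.75 analysable patients per arm, and 86.5% with all 75. The number of patients is not the problem.

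**Effect of selective erasure.** Let p be the share of an arm erased, and d the amount, in SD after baseline adjustment, by which those patients are more anxious than the ones who remain. The full arm mean equals the mean of those who remain plus p × d, so analysing only those who remain understates that arm's anxiety by p × d. With the same d in both arms, the shift in the treatment difference is

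shift = (p in VR arm − p in control arm) × d.

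The protocol gives neither p nor d, so every value below is an assumption.

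| Net difference in p | d (SD) | Shift (SD) | Share of 0.5 SD target |
|---|---|---|---|
| 5% | 0.5 | 0.05 × 0.5 = 0.025 | 5% |
| 5% | 1.0 | 0.05 × 1.0 = 0.05 | 10% |
| 15% (stress case) | 1.0 | 0.15 × 1.0 = 0.15 | 30% |

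If 15% were erased in the VR arm and 10% among controls with the same d, the net difference is 5% and the first two rows apply. If more anxious controls were erased than VR patients, the sign reverses.

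With no true effect, and with all the erasure in the VR arm, the two-sided rejection rate moves from 5% to 5.3% in the first row and 6.1% in the second. It reaches 14.2% in the stress case (normal approximation, 75 controls against 75 × (1 − p) VR patients).

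**Adverse-effect record.** Assume a true symptom rate of 10% among 75 VR patients, that is 7.5 affected.

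- A quarter of the affected erased: 5.625 / 73.125 = 7.7% observed.
- Half of the affected erased: 3.75 / 71.25 = 5.3% observed.

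These rates are also assumed. They show only how the record would change if symptoms and erasure were linked.

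**The case against.** The case against has real force.

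- **Destruction is not automatic.** A reader might infer that every withdrawal destroys all data. The sentence describes an option, and it can be read as granting two rights that a patient may use separately. The consent form was not available for this review and may already separate them. This stands: the finding is that the protocol does not make the separation, not that erasure will always follow.
- **A stopped session is not a withdrawal.** A reader might infer that VR patients who feel unwell drop out of the data. Risk and benefits ends the session and involves the doctor; it does not end follow-up. Data are lost only if the patient also leaves and the data are then destroyed, and no section links these steps.
- **Participant flow is not lost.** Allocation runs from a statistician's sequence and numbered envelopes, and patients have ID numbers, so counts by arm can survive deletion of outcomes. The CONSORT commitment points the same way. A sensitivity analysis with worst-case or shifted values also stays possible where the arm is known, though with less information.
- **The direction is not established.** A reader might infer that the bias favours VR. Participants know their arm, and anxious controls disappointed by their allocation could also leave, which would work against VR.
- **The stress case is extreme.** The dropout allowance covers both arms and is not a rate of deletion requests. Baseline adjustment also removes part of any anxiety difference. VR exposure is short (5 to 10 minutes), and patients with a history of motion sickness or seizures are excluded.

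Handling of withdrawals is often left to the statistical analysis plan. That does not dispose of the point, because destroyed values are out of the plan's reach.

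**Conclusion.** The concern holds in a limited form. The protocol's only stated withdrawal route joins leaving with destruction of data, at any time, and no other section keeps what was collected before. Randomised patients who leave may therefore have T1 and T2 values erased, at a cost to the as-randomised analysis and, in the VR arm, to the adverse-effect record. Bias arises only if erasure is related to treatment or anxiety, and its direction cannot be stated in advance.

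A reasonable illustration is a shift of 0.025 to 0.05 SD, or 5% to 10% of the target effect. It rests on an assumed net between-arm difference of 5% and an assumed excess anxiety of 0.5 to 1 SD after baseline adjustment. The 0.15 SD figure needs the whole 15% allowance to be selective erasure in the VR arm alone, with none among controls; it should not be quoted as an expected bias. The sample size of 150 is unaffected. The change is worth making because it is cheap now and destroyed data cannot be recovered.

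**What to change.** In Participant rights and in the consent form, make two separate choices:

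1. Withdrawal means no further data collection. Data already collected are kept and analysed in the randomised arm, as the consent allows.
2. Deletion of collected data happens only on a separate, explicit request.

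State in Risk and benefits that stopping the VR session is not by itself withdrawal from follow-up. Add a sentence to Data storage that refers to these choices. Report the aggregate number of withdrawals and of deletions by arm and time point, and keep no individual health data after a deletion request. Patients who do ask for deletion will still be lost to the analysis; the change limits the loss to them.

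The cost is wording in the protocol and consent form, plus one more option to explain to patients. The right to deletion remains. The wording is subject to ethics approval, which the protocol describes as still to be obtained.

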### PRIVACY

Each consenting patient will be assigned a participant ID number which will be used on all study documents. The spreadsheet linking the study number with the participant's personal identifying information will be kept separate from all other documents. Participants will not be individually identifiable in the reporting of the data.

## DATA STORAGE

Electronic data will be kept on the password-protected in both the King Abdulaziz University Hospital research server and the University of Newcastle research server. Hard copy data will be stored in a locked cabinet in the office of the Chief Investigator. Only the named researchers will have access to the identifiable research data. The data will be kept for at least 15 years at the University of Newcastle before being destroyed as per policy and protocol (The University of Newcastle, 2020).
